4.4.1.1.7 Ongoing

Ongoing is derived from the last daily intensity of the solicited period computed as described in [Section 4.4.1.1.1](#) and the maximum intensity on the ongoing period. The investigator's ongoing flag is not used because the measurement would determine the ongoing status of the reaction.

Note: a reaction could be derived as not ongoing for the analysis despite being considered as ongoing by the investigator (eg, when the maximum measurement after D7 is > 0 mm but < 25 mm for 12 to 17 years of age). If the last daily intensity of the solicited period is at least Grade 1 and maximum intensity on the ongoing period is also at least Grade 1, then the reaction is considered ongoing. In any other cases the reaction will not be considered as ongoing.

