4.4 Derived Endpoints: Calculation Methods

4.4.1 Safety

4.4.1.1 Solicited Reactions

4.4.1.1.1 Daily Intensity

All daily records for solicited reactions will be derived into daily intensity according to the following classification: None, Grade 1, Grade 2, Grade 3, or Missing.

For measurable injection site reactions (Erythema/Swelling/Induration/Bruising):

- For subjects 6 months to 11 years of age

Grade 1: > 0 to < 25 mm

Grade 2: ≥ 25 to < 50 mm

Grade 3: ≥ 50 mm

- For subjects 12 to 17 years of age

Grade 1: ≥ 25 to ≤ 50 mm

Grade 2: ≥ 51 to ≤ 100 mm

Grade 3: > 100 mm

For measurable systemic reactions (Fever):

- For subjects 6 months to < 36 months of age

Grade 1: $\geq 38.0^{\circ}\text{C}$ to $\leq 38.5^{\circ}\text{C}$, or $\geq 100.4^{\circ}\text{F}$ to $\leq 101.3^{\circ}\text{F}$

Grade 2: $> 38.5^{\circ}\text{C}$ to $\leq 39.5^{\circ}\text{C}$, or $> 101.3^{\circ}\text{F}$ to $\leq 103.1^{\circ}\text{F}$

Grade 3: $> 39.5^{\circ}\text{C}$, or $> 103.1^{\circ}\text{F}$

- For subjects 3 to 17 years of age

Grade 1: $\geq 38.0^{\circ}\text{C}$ to $\leq 38.4^{\circ}\text{C}$, or $\geq 100.4^{\circ}\text{F}$ to $\leq 101.1^{\circ}\text{F}$

Grade 2: $\geq 38.5^{\circ}\text{C}$ to $\leq 38.9^{\circ}\text{C}$, or $\geq 101.2^{\circ}\text{F}$ to $\leq 102.0^{\circ}\text{F}$

Grade 3: $\geq 39.0^{\circ}\text{C}$, or $\geq 102.1^{\circ}\text{F}$

For the derivation of daily intensities the following sequential steps will be applied:

Solicited reactions (except Fever/Pyrexia) with an investigator occurrence recorded as “No” and with all daily records missing then all daily intensities will be derived as “None”.

For non-measurable solicited reactions, daily intensities will correspond to daily records reported in the clinical database. For measurable solicited reactions the daily measurements reported in the clinical database will be converted based upon the intensity scales defined in the protocol; this assumes a reaction that is too large to measure (non-measurable, “NM”) is Grade 3. Note the intensity could be considered “None” (not a reaction) in the analysis despite being considered a reaction by the investigator (eg, swelling measurement > 0 mm but < 25 mm in 12 to 17 years of age).

Note: The maximum intensity on the ongoing period is derived from the record of the maximum intensity/measurement after the end of the solicited period following the rule described above.

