4.4.1.1.6 Overall Number of Days of Occurrence

If a reaction is ongoing at the end of the solicited period, then the overall number of days of occurrence is derived from the daily intensities and the stop date of the reaction after the end of the solicited period. The overall number of days of occurrence is:

- $(\text{stop date} - \text{vaccination date}) + (\text{number of days of occurrence within the solicited period}) - \text{length of the solicited period} + 1$.

If the stop date is missing or incomplete (containing missing data [MD]), the overall number of days of occurrence will be considered as Missing.

Table 4.3: Categories for overall number of days of occurrence

Injection Site Reactions	Systemic Reactions
1-3 days	1-3 days
4-7 days	4-7 days
≥ 8 days	≥ 8 days
Missing	Missing

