5.3 Handling of Missing Data and Outliers

5.3.1 Safety

No replacement will be done. Nevertheless, missing relationship will be considered as related at the time of the statistical analysis. No search for outliers will be performed. In all subject listings, partial and missing data will be clearly indicated as missing.

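### A solicited reaction graded on Day 7 is classed as not ongoing when its later intensity is missing, and by inference its duration then ends at Day 7 even if a later stop date is recorded

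*SAP*

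**What the plan says.** In SAP 4.4.1.1.1 (Daily Intensity), each daily record of a solicited reaction "will be derived into daily intensity according to the following classification: None, Grade 1, Grade 2, Grade 3, or Missing". Missing is thus a value in its own right. The intensity after Day 7 has a single source: "The maximum intensity on the ongoing period is derived from the record of the maximum intensity/measurement after the end of the solicited period".

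SAP 4.4.1.1.7 (Ongoing) sets the test for ongoing status as follows: "last daily intensity of the solicited period is at least Grade 1 and maximum intensity on the ongoing period is also at least Grade 1". All remaining situations are settled in one sentence: "In any other cases the reaction will not be considered as ongoing". The investigator's opinion is set aside: "The investigator's ongoing flag is not used because the measurement would determine the ongoing status of the reaction". The illustration given there is a recorded size above 0 but below 25 mm at 12 to 17 years, which is not a graded reaction in that age band.

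SAP 4.4.1.1.6 (Overall Number of Days of Occurrence) brings in the stop date for a reaction that is ongoing. It names one route to a missing result: "If the stop date is missing or incomplete (containing missing data [MD]), the overall number of days of occurrence will be considered as Missing". SAP 4.4.1.1.5 defines the other available count, the graded days within D0-D7.

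For missing solicited intensities, SAP 5.3.1.4 points back to 4.4.1.1.1. The missing-record rule there concerns a reaction other than fever that the investigator marked as not having occurred: "with all daily records missing then all daily intensities will be derived as" None. A reaction too large to measure is taken as Grade 3. Neither rule covers a reaction graded on Day 7 with no later intensity.

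**The concern.** The reason the SAP gives for ignoring the investigator's flag is that a measurement decides the matter. That reason fails when the measurement is absent, yet the catch-all still returns a definite answer: not ongoing. An absent later intensity is handled in the same way as a recorded one below Grade 1.

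Two outputs are at stake: the number of reactions ongoing after Day 7, and the overall-duration categories of SAP Table 4.3. For a reaction that did persist, the default can only lower both. How long reactions last is part of what a dose-selection study describes, so a one-sided shortening that no table reveals is worth removing.

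**Working it through.** **Inputs.** Solicited period D0-D7, hence length 8 days (SAP Table 4.2 has 8 days as its top category). Categories of overall duration: 1-3, 4-7, at least 8 days, Missing (SAP Table 4.3). With days numbered from vaccination, the SAP 4.4.1.1.6 formula is:

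overall days = stop day + graded days within D0-D7 - 8 + 1.

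**Step 1: the formula itself.** A continuous reaction that starts on day k (0 to 7) and persists past Day 7 has 8 - k graded days in the period. The formula gives stop + (8 - k) - 8 + 1 = stop - k + 1, which is the true duration. The formula is sound. The fault lies in the rule that decides when it is used.

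**Step 2: one reaction under four states of the data.** Onset D5, graded on D5, D6 and D7, stop D12, true duration 12 - 5 + 1 = 8 days.

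| Later maximum intensity | Stop date | Status | Overall days | Category |
|---|---|---|---|---|
| Grade 1 or higher | D12 | ongoing | 12 + 3 - 8 + 1 = 8 | at least 8 |
| Missing | D12 | not ongoing | 3 | 1-3 |
| Grade 1 or higher | missing | ongoing | Missing | Missing |
| Missing | missing | not ongoing | 3 | 1-3 |

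The second row discards a stop date that is in the database. Rows three and four show the inconsistency: taking away one more piece of information changes the result from Missing to a definite and shorter duration.

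**Step 3: when the category changes.** If the later intensity is missing, the count is 8 - k whatever the stop date.

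| Onset | Count reported | True, stop D8 | True, stop D10 | True, stop D12 | True, stop D14 | Stops at which the category falls |
|---|---|---|---|---|---|---|
| D0 | 8 | 9 | 11 | 13 | 15 | none |
| D1 | 7 | 8 | 10 | 12 | 14 | all four |
| D2 | 6 | 7 | 9 | 11 | 13 | D10, D12, D14 |
| D3 | 5 | 6 | 8 | 10 | 12 | D10, D12, D14 |
| D4 | 4 | 5 | 7 | 9 | 11 | D12, D14 |
| D5 | 3 | 4 | 6 | 8 | 10 | all four |
| D6 | 2 | 3 | 5 | 7 | 9 | D10, D12, D14 |
| D7 | 1 | 2 | 4 | 6 | 8 | D10, D12, D14 |

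The count is too low in all 32 combinations, and the category falls in 0 + 4 + 3 + 3 + 2 + 4 + 3 + 3 = 22. These are illustrative patterns, not frequencies.

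**Step 4: how the SAP treats a comparable case.** SAP 4.4.1.2.5 derives the duration of unsolicited non-serious events from start and stop dates alone, and sets it to missing only when a date is missing. No intensity has to be present first.

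**The case against.** Several counter-arguments have weight.

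- **The cut at Day 7 is inferred.** SAP 4.4.1.1.6 does not say what overall duration a non-ongoing reaction receives. This stands. The classification as not ongoing is explicit; the shortened duration follows because the D0-D7 count is the only other one defined.
- **Not ongoing is right for a reaction that ended on Day 7.** Such a reaction has no later record to give. This also stands, and the fix must allow for it. It does not explain away a recorded stop date after Day 7.
- **The investigator's flag is ignored for good reason.** At 12 to 17 years a size below 25 mm is not graded, so a flag or stop date alone does not show a graded reaction. This is correct and limits the remedy.
- **Data collection should make the case uncommon.** Diaries run until resolution (Protocol 9.1.3.2), are reviewed at visits (Protocol 5.1.4) and clarified verbally if incomplete (Protocol 13.2), and a blind data review precedes lock (SAP 5.6). This argues for low frequency. It does not supply a rule.
- **Little depends on it.** Occurrence, onset and maximum intensity within D0-D7 do not use the ongoing rule, nor do the criteria of the early safety data review (Protocol 5.1.6). All analyses are descriptive. This stands.

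A reader might go further in three ways that the documents do not support:

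- That a missing Day 7 record has the same effect. The last daily intensity can be read as the last one available, and presence on Day 7 is then not recorded.
- That a given share of prolonged reactions is misclassified. No rate of missing later intensities is stated.
- That the SAP breaks its own statement "No replacement will be done" (SAP 5.3.1). No recorded value is replaced; a derived status is given a prespecified default. The default has the effect of assuming resolution, but calling it a breach is too strong.

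**Conclusion.** The point holds for one situation: a reaction of at least Grade 1 on Day 7 whose maximum intensity after the solicited period was due but not recorded. The SAP classes it as not ongoing and, by inference, gives it a definite duration that leaves out every day after Day 7. In the worked example this is 3 days instead of 8. A continuous reaction from D0 loses days but stays in the category of at least 8 days, and some shorter reactions also keep their category.

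The conclusion rests on Missing falling under the catch-all, which is the plain reading, and on non-ongoing reactions receiving the D0-D7 count. The number of children affected cannot be estimated from the documents. Only the ongoing and overall-duration outputs are touched. It is a minor point, worth correcting because the error runs one way and the correction is cheap.

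**What to change.** Amend SAP 4.4.1.1.7 for reactions of at least Grade 1 on Day 7 with a missing later maximum intensity, so that they no longer default to not ongoing:

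- If a complete stop date after Day 7 exists, treat the reaction as ongoing and apply the SAP 4.4.1.1.6 formula.
- Otherwise set both ongoing status and overall duration to Missing, unless the record shows that the reaction ended by Day 7. In that case no later intensity was due and not ongoing stands.
- For measurable injection site reactions at 12 to 17 years, set both to Missing when the later size is missing, even if a later stop date exists. The same exception for a reaction that ended by Day 7 applies.
- Keep not ongoing for a recorded later value below Grade 1, and continue to leave the investigator's flag out.

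One further sentence in SAP 4.4.1.1.6 should state the overall duration of a reaction that is not ongoing.

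The cost is a few sentences and a small programming change, with no new data. The downside is a few more Missing durations. Their number depends on how the case report book separates a reaction that ended on Day 7 from one with a missing later record, which the documents do not show.

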4.4.1.2 Unsolicited Non-serious AEs

Unsolicited AEs include non-serious unsolicited AEs and SAEs. This subsection only covers the endpoints for unsolicited non-serious AEs.

4.4.1.2.1 Occurrence

An observation will be considered an event if it has at least a verbatim term and is not a Grade 0 intensity event. Grade 0 events should be included in the listing "Unsolicited non-serious adverse events not included in the safety analysis."

4.4.1.2.2 Intensity

Intensity for unsolicited non-serious AE will be derived according to the following classification: None, Grade 1, Grade 2, Grade 3, or Missing.

If the unsolicited non-serious AE is measurable and its preferred term is part of the list of solicited reactions, then the measurement is derived based upon and following the same rule as the intensity scales defined in the protocol for that measurable injection site or systemic reaction.

Note: the intensity could be considered "None" (not a reaction) in the analysis despite being considered a reaction by the investigator (eg, swelling measurement > 0 mm but < 25 mm for 12 to 17 years of age). Intensity for the other unsolicited non-serious AEs will correspond to the value reported in the CRB.

The maximum intensity corresponds to the highest intensity for a unique term.

4.4.1.2.3 Vaccination

Last vaccination before an unsolicited non-serious AE is derived from the visit numbers provided in the clinical database and is calculated as follows:

- If an unsolicited non-serious AE has a non-missing visit number, the visit number should be used to determine the last vaccination before the unsolicited non-serious AE.
- If the visit number is missing, then the start date should be used to determine the last vaccination before the unsolicited non-serious AE.

4.4.1.2.4 Time of Onset

Time of onset is derived from the start date of the unsolicited non-serious AE provided in the clinical database and the date of last vaccination:

- Start date of the unsolicited non-serious AE – date of vaccination.

The time of onset should be considered as missing only if one or both of the dates are missing or partially missing.

The unsolicited non-serious AEs will be analyzed “Within 28 days”, which corresponds to AEs with a time of onset between 0 and 28 days after vaccination or missing. An AE with missing time of onset will be considered to have occurred just after the vaccination indicated by the visit number (See [Section 4.4.1.2.3](#)), so will be included in these tables.

Note: Unsolicited non-serious AE that occurred before vaccination (negative time of onset) or with a time of onset higher than defined above (> 28 days) will not be included in analysis, but will be listed separately.

Time of onset will be displayed as follows:

- D0-D3
- D4-D7
- D8-D14
- $\geq D15$
- Missing

4.4.1.2.5 Duration

Duration is derived from the start and stop dates of the unsolicited non-serious AE provided in the clinical database:

- Stop date of unsolicited non-serious AE - start date of unsolicited non-serious AE + 1.

The duration should be considered as missing only if one or both of the start and stop dates of the unsolicited non-serious AE is missing or partially missing.

Duration will be displayed by period as following:

- 1-3 days

- 4-7 days
- 8-14 days
- ≥ 15 days
- Missing

4.4.1.3 SAEs

4.4.1.3.1 Vaccination

Last vaccination before an SAE is derived from the last visit numbers provided in the clinical database and is calculated as follows:

- If an SAE has a non-missing visit number, the visit number should be used to determine the last vaccination before the SAE
- If the visit number is missing, then the start date should be used to determine the last vaccination before the SAE.

4.4.1.3.2 Time of Onset

Time of onset will be computed using the same methodology as for unsolicited non-serious AEs described in [Section 4.4.1.2.4](#).

SAEs will be analyzed throughout the study using the following periods:

- During post-Dose period (within 28 days after any injection)
- During the whole study (ie, all SAEs occurred during the study)

4.4.1.3.3 Duration

Duration will be computed using the same methodology as for unsolicited non-serious AEs described in [Section 4.4.1.2.5](#).

4.4.1.3.4 Intensity

The intensity for SAE is the same as the intensity for non-serious AE as described in [Section 4.4.1.2.2](#).

4.4.1.4 Other Safety Endpoints

4.4.1.4.1 Action Taken

This information will be summarized as collected, including missing observations. No derivation or imputation will be done.

4.4.1.4.2 Seriousness

This information will be summarized as collected. No derivation or imputation will be done.

4.4.1.4.3 Outcome

This information will be summarized as collected. No derivation or imputation will be done.

4.4.1.4.4 Causality

This information will be summarized as collected. An adverse reaction (AR) is defined as an unsolicited non-serious AE or an SAE with causality to the vaccine. Missing causality (relationship) will be handled as described in [Section 5.3.1.2](#).

4.4.1.4.5 AEs Leading to Study Discontinuation

A flag is available in the clinical database for all AEs in order to identify AEs leading to discontinuation.

In general, the items that are counted are:

- Disposition table: A subject who has, on the termination form, the reason for early termination “adverse event” checked.
- Safety overview table: A subject who has either on the termination form, the reason for early termination “adverse event” checked or lists an AE on an AE page (solicited, unsolicited, or SAE) that has “Reaction Leading to Termination” or “Event Leading to Termination” or “Serious Adverse Event Leading to Termination” checked that is at least Grade 1 and is within the time period indicated. Note: If the Grade is below 1, the AE will be excluded from the list of AEs leading to study discontinuation.
- System organ class (SOC)/Preferred term (PT) table: An event (solicited, unsolicited, or SAE) that has “Cause Study Termination” or “Caused Study Discontinuation” checked that is at least Grade 1 and is within the time period indicated.

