### 9.1.2 Safety Endpoints

The endpoints for the evaluation of safety are:

- Occurrence, nature (Medical Dictionary for Regulatory Activities [MedDRA] preferred term [PT]), duration, intensity, and relationship to vaccination of any unsolicited systemic AEs reported in the 30 minutes after each vaccination.
- Occurrence, time to onset, number of days of occurrence, intensity, action taken, and whether the reaction led to early termination from the study, of solicited (prelisted in the subject's diary card and CRB) injection site reactions and systemic reactions occurring up to 7 days after each vaccination.
- Occurrence, nature (MedDRA system organ class [SOC] and PT), time to onset, duration, intensity, relationship to vaccination (for systemic AEs only), and whether the event led to early termination from the study, of unsolicited AEs up to 28 days after each vaccination.
- Occurrence, nature (MedDRA SOC and PT), time to onset, seriousness criteria, relationship to vaccination, outcome, and whether the event led to early termination from the study, of SAEs (including AESIs) throughout the study.
- Occurrence, nature (MedDRA PT), time to onset, and relationship to vaccination of AESIs throughout the study.

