5.3.1.4 Intensity

For solicited reactions, missing intensities will be handled as described in [Section 4.4.1.1.1](#). For unsolicited non-serious AEs, missing intensities will remain missing and will not be imputed.

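### The by-term table of adverse events leading to discontinuation, read literally, leaves out flagged events whose intensity is missing

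*SAP*

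**What the plan says.** SAP 4.4.1.4.5 sets a separate counting rule for each of three outputs.

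- **Disposition table.** It counts "A subject who has, on the termination form, the reason for early termination" given as an adverse event. Grade plays no part.
- **Safety overview.** It counts "A subject who has either on the termination form, the reason for early termination" given as an adverse event, or a child with a flagged event on an AE page. The AE-page route requires at least Grade 1, and a note follows: "If the Grade is below 1, the AE will be excluded from the list of AEs leading to study discontinuation".
- **SOC/PT table.** It counts only events with the flag "checked that is at least Grade 1 and is within the time period indicated". There is no termination-form route.

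The grade being tested is a derived variable. SAP 4.4.1.2.2 states: "Intensity for unsolicited non-serious AE will be derived according to the following classification: None, Grade 1, Grade 2, Grade 3, or Missing". SAP 4.4.1.3.4 extends this to serious events: "The intensity for SAE is the same as the intensity for non-serious AE as described in" the section for non-serious events. For unsolicited non-serious AEs, SAP 5.3.1.4 says that "missing intensities will remain missing and will not be imputed".

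The protocol endpoint (9.1.2) includes "whether the event led to early termination from the study, of unsolicited AEs up to 28 days after each vaccination". It sets no minimum grade.

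**The concern.** Whether an event ended a child's participation is a fact about the child, recorded by a flag. It is a listed safety endpoint in its own right. Filtering the flag by intensity makes its reporting depend on a different field being filled in.

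The SOC/PT table is the one output of the three that says which event was responsible. If an event drops out there, a reader can see from the disposition table that a child left because of an adverse event and find no matching row. Most arms have 10 or 30 children and the study is meant to inform the Phase III dosage, so a single named event can be of interest.

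**Working it through.** The plan states no figure on this point. The check is to follow a flagged event, with onset inside the period, through the three rules.

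**Step 1: which intensities can occur.** Under SAP 4.4.1.2.2 and 4.4.1.3.4 the derived value is None, Grade 1 to 3, or Missing. None arises from the grading scales: for example a swelling above 0 but under 25 mm at 12 to 17 years, or a temperature below 38.0°C. Missing arises when no intensity was recorded.

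**Step 2: apply each rule.** The termination form is assumed to give an adverse event as the reason.

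| Derived intensity | Disposition | Overview, form route | Overview, AE-page route | SOC/PT table |
|---|---|---|---|---|
| Grade 1, 2 or 3 | counted | counted | counted | counted |
| Missing | counted | counted | not counted (read literally) | not counted (read literally) |
| None | counted | counted | not counted | not counted |

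**Step 3: compare the Missing row with the rest of the plan.**

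- SAP 4.4.1.2.1 asks two things of an unsolicited non-serious event: a verbatim term, and a grade other than 0. A missing grade passes, so the event belongs in the general AE tables. The discontinuation table then omits it.
- Within the overview item, the condition and the note disagree. Missing is not Grade 1 or more, so the condition excludes it. It is not below 1 either, so the note does not.
- In protocol 9.1.2, intensity and leading to early termination are separate attributes of unsolicited AEs. For SAEs, intensity is not among the listed attributes.
- Elsewhere the SAP keeps events with missing information. A missing causality assessment is treated as related (5.3.1.2), and an event with missing onset time stays in the analysis (4.4.1.2.4 and 5.3.1.5).

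**Step 4: what one event looks like.** This is an illustration only, and the one omitted event is an assumption. It uses the plan's Clopper-Pearson interval: lower limit = Beta⁻¹(0.025; x, n−x+1), upper limit = Beta⁻¹(0.975; x+1, n−x). For x = 0 the lower limit is 0 and the upper limit is 1 − 0.025^(1/n).

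| Arm size | Event omitted | Event shown |
|---|---|---|
| 10 | 0/10, 95% CI 0.0 to 30.8% | 1/10 = 10.0%, 0.3 to 44.5% |
| 30 | 0/30, 0.0 to 11.6% | 1/30 = 3.3%, 0.1 to 17.2% |
| 45 | 0/45, 0.0 to 7.9% | 1/45 = 2.2%, 0.1 to 11.8% |

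The intervals overlap heavily. What changes is whether a named event appears at all.

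**The case against.** **The child is not lost.** A reader might infer that these discontinuations disappear from the report. The documents do not support that. The disposition table and the form route of the overview have no grade condition, and the protocol makes that route dependable: 5.2.10 ranks an adverse event first among the reasons for termination, and 5.2.8 has a voluntary withdrawal over safety concerns recorded under that reason. This stands, and it confines the point to the SOC/PT table and the AE-page route.

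**A reaction under 25 mm at 12 to 17 years is excluded on purpose.** A reader might take this exclusion for an error too. Protocol Table 9.3 starts Grade 1 at 25 mm for that age. SAP 4.4.1.1.1 and 4.4.1.2.2 say openly that a smaller measurement may not count as a reaction in the analysis, even if the investigator thought it one. That follows the plan's own scale and is not in itself an error. It reaches only the 12 to 17 year part of the 130 children in Groups 12 and 13 (70 + 60), who get one dose. One gap remains: the separate listing in SAP 4.4.1.2.1 covers Grade 0 unsolicited non-serious events, and no equivalent is stated for solicited reactions or SAEs.

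**A missing grade on such an event is unlikely.** Protocol 9.1.3.3 asks for the intensity of every unsolicited AE, 11.1 requires missing information to be explained, 13.4.1 requires queries to be closed before database lock, and 5.1.4 requires follow-up of AEs that caused discontinuation. This stands. It makes the case rare but does not say how to handle it.

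**The outputs count different things.** The overview counts children and the SOC/PT table counts events, so totals need not match. True, but a child counted with no event behind the count is a different kind of mismatch.

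**Conclusion.** The point holds in a narrow form. Read literally, the grade condition removes a flagged AE or SAE with missing intensity from the SOC/PT discontinuation table and from the AE-page route of the overview. For unsolicited non-serious AEs this conflicts with the SAP's own definition of an event; for these and for SAEs it adds a condition that the protocol endpoint does not have. The by-term count can only be too low, and it can disagree with the other two tables.

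This is a minor correction that will rarely be triggered. A reader might want to express it as a share of all discontinuations. The documents give neither an expected rate of discontinuation for adverse events nor a rate of missing intensity, so no such percentage can be supported. The conclusion rests on reading the Grade 1 condition literally, and on reading the grade test in the overview as attached to the AE-page route alone.

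**What to change.** In the overview and SOC/PT items of SAP 4.4.1.4.5, replace the Grade 1 condition with: *not Grade 0; missing intensity is included and shown as missing*. The note in the overview item can then stay as it is.

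Add a listing of every flagged event excluded because its derived intensity is None. It should include solicited reactions and SAEs, so that the disposition, overview and SOC/PT tables can be reconciled child by child.

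The cost is a few words of SAP text, a small change to the table programs and one short listing. No new data are needed, and the grading scales stay as they are.
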